Appendix 2 Microbiology

Method of Collection of Urine Specimens:

To obtain a clean catch sample of urine from a female patient, a thorough cleansing of the periurethral area is essential before specimen collection. Wash the area with a disinfectant and make all efforts to avoid any contact until urination is complete.

All patients should void the first part of the specimen into the toilet, then collect the remainder of the specimen in a sterile container.

Culture and Susceptibility testing

All gram-negative pathogens will be tested locally for antimicrobial susceptibility, as appropriate.

.

Appendix 3 Patient Symptom Assessment Questionnaire (PSAQ)

INSTRUCTIONS: Do you have any of the following symptoms due to your current UTI? If yes, indicate severity by checking Mild, Moderate or Severe. If you do not have a symptom, or if a symptom is present but related to another known condition, then check No Symptom.

CHECK ONLY ONE RESPONSE PER QUESTION. REFER TO PAGE 2 FOR GUIDANCE SPECIFIC TO QUESTIONS 2 AND 4.

		Severity (check one)		k one)	Complete the below on DAY 12 if you still have symptoms.	
		Mild	Moderate	Severe	No symptom/ Resolved or returned to the same condition as before you had a UTI	Question: What is the impact of your remaining symptom(s) on your daily activities (i.e., how bothersome are the symptoms)?
1	Gross hematuria (visible blood in your urine)					☐ Not at all ☐ Not significantly bothersome ☐ Moderately bothersome ☐ Severely bothersome
2	Pain (uncomfortable pressure) in the lower abdomen/pelvic area*					☐ Not at all ☐ Not significantly bothersome ☐ Moderately bothersome ☐ Severely bothersome
3	Burning (dysuria) when passing urine					☐ Not at all ☐ Not significantly bothersome ☐ Moderately bothersome ☐ Severely bothersome
4	Frequency, urgency of urination or going to the toilet very often**					☐ Not at all ☐ Not significantly bothersome ☐ Moderately bothersome ☐ Severely bothersome

ADDITIONAL GUIDANCE FOR QUESTIONS 2 AND 4

- * Pain (uncomfortable pressure) in the lower abdomen/pelvic area
- Choose "No symptom" if no significant pain or back to before you had a UTI
- · Choose "Mild" if occasional pain, but usually overlooked
- · Choose "Moderate" if considerable pain, but tolerable
- · Choose "Severe" if severe pain requiring treatment
- **For frequency/urgency of urination
- Choose "No symptom" if you can hold your urine for more than two hours during the daytime, or you can hold your urine as long as you could before you had a UTI
- . Choose "Mild" if more frequent than normal, but can hold your urine for 1-2 hours
- Choose "Moderate" if considerably more frequent than normal, i.e., cannot hold urine for 1 hour
- . Choose "Severe" if very frequent, i.e. cannot even hold your urine for 30 minutes

Source: Adapted from Wageniehner et al, Ceftazidime-avibactam versus doripenem for the treatment of complicated urinary tract infections including acute pyelonephritis: RECAPTURE, a phase 3 randomized trial program. CID 2016:63; 754-762.

Appendix 4 Ciprofloxacin Tablets – USPI

HIGHLIGHTS OF PRESCRIBING INFORMATION

These highlights do not include all the information needed to use CIPRO safely and effectively. See full prescribing information for CIPRO.

CIPRO® (ciprofloxacin hydrochloride) tablet, for oral use

CIPRO® (ciprofloxacin hydrochloride), for oral suspension

Initial U.S. Approval: 1987

WARNING: SERIOUS ADVERSE REACTIONS INCLUDING TENDINITIS, TENDON RUPTURE, PERIPHERAL NEUROPATHY, CENTRAL NERVOUS SYSTEM EFFECTS AND EXACERBATION OF MYASTHENIA GRAVIS

See full prescribing information for complete boxed warning.

- Fluoroquinolones, including CIPRO*, have been associated with disabling and potentially irreversible serious adverse reactions that have occurred together (5.1), including:
- Tendinitis and tendon rupture (5.2) Peripheral neuropathy (5.3)
- o Central nervous system effects (5.4)

Discontinue CIPRO immediately and avoid the use of fluoroquinolones, including CIPRO, in patients who experience any of these serious adverse reactions (5.1)

- Fluoroquinolones, including CIPRO, may exacerbate muscle weakness in patients with myasthenia gravis. Avoid CIPRO in patients with known history of myasthenia gravis. (5.5)
- Because fluoroquinolones, including CIPRO, have been associated with serious adverse reactions (5.1-5.15), reserve CIPRO for use in patients who have no alternative treatment options for the following indications:

 Acute exacerbation of chronic bronchitis
 O Acute uncomplicated cystitis (1.11)
 Acute sinusitis (1.12)

----- RECENT MAJOR CHANGES -----

--- INDICATIONS AND USAGE -----

Boxed Warning	M/2016 Indications and Usage (1.10, 1.11, 1.	2) M/2016 Dosage and Administration, Dosage in Adults (2.1) M/201
Warnings and Pred	eautions (5.1)	M/2016

CIPRO is a fluoroquinolone antibacterial indicated in adults (≥18 years of age) with the following infections caused by designated, susceptible bacteria and in pediatric patients where indicated: • Skin and Skin Structure Infections (1.1)

- Bone and Joint Infections (1.2)
- Complicated Intra-Abdominal Infections (1.3)
- Infectious Diarrhea (1.4)
- Typhoid Fever (Enteric Fever) (1.5)
- Uncomplicated Cervical and Urethral Gonorrhea (1.6)
- Inhalational Anthrax post-exposure in adult and pediatric patients (1.7)
- Plague in adult and pediatric patients (1.8)
- Chronic Bacterial Prostatitis (1.9)
- Lower Respiratory Tract Infections (1.10)

 Acute Exacerbation of Chronic Bronchitis

every 12 hours

single dose

every 12 hours

10 days

single dose

60 days

Complicated UTI and Pyelonephritis in Pediatric Patients • Acute Sinusitis (1.12)

Usage

To reduce the development of drug-resistant bacteria and maintain the effectiveness of CIPRO and other antibacterial drugs, CIPRO should be used only to treat or prevent infections that are proven or strongly suspected to be caused by bacteria. (1.13)

Infection	Dose	Frequency	Duration
Skin and Skin Structure	500 -750 m	g every 12 hours	7 to 14
			days
Ad	ult Dosage Gu	idelines	
Infection	Dose	Frequency	Duration
Bone and Joint	500-750 mg	every 12 hours	4 to 8 weeks
Complicated IntraAbdominal	500 mg	every 12 hours	7 to 14 days
Infectious Diarrhea	500 mg	every 12 hours	5 to 7 days

500 mg

250 mg

500 mg

-- DOSAGE AND ADMINISTRATION --Adult Dosage Guidelines

Confidential

Typhoid Fever

(postexposure)

Uncomplicated Gonorrhea

Inhalational anthrax

Plague	500-750 mg	every 12 hours	14 days
Chronic Bacterial Prostatitis	500 mg	every 12 hours	28 days
Lower Respiratory Tract	500 -750 mg	every 12 hours	7 to 14 days
Urinary Tract	250-500 mg	every 12 hours	7 to 14 days
Acute Uncomplicated Cystitis	250 mg	every 12 hours	3 days
Acute Sinusitis	500 mg	every 12 hours	10 days

- Adults with creatinine clearance 30–50 mL/min 250–500 mg q 12 h (2.3)
- Adults with creatinine clearance 5–29 mL/min 250–500 mg q 18 h (2.3)
- Patients on hemodialysis or peritoneal dialysis 250–500 mg q 24 h (after dialysis) (2.3)

Pediatric Oral Dosage Guidelines						
Infection	Dose	Frequency	Duration			
Complicated UTI and Pyelonephritis (1 to 17 years of age)	10–20 mg/kg (maximum 750 mg per dose)	Every 12 hours	10–21 days			
Inhalational Anthrax (Post-Exposure)	15 mg/kg (maximum 500 mg per dose)	Every 12 hours	60 days			
Plague	15mg/kg (maximum 500 mg per dose)	Every 8 to 12 hours	10–21 days			

----- DOSAGE FORMS AND STRENGTHS

- Tablets: 250 mg, 500 mg (3)
- Oral Suspension: 5% (250 mg/5 mL), 10% (500 mg/5 mL) (3)

----- CONTRAINDICATIONS -----

- Known hypersensitivity to CIPRO or other quinolones (4.1, 5.6, 5.7)
- Concomitant administration with tizanidine (4.2)

---- WARNINGS AND PRECAUTIONS -----

- Hypersensitivity and other serious reactions: Serious and sometimes fatal reactions (for example, anaphylactic reactions) may occur after the first or subsequent doses of CIPRO. Discontinue CIPRO at the first sign of skin rash, jaundice or any sign of hypersensitivity. (4.1, 5.6, 5.7)
- Hepatotoxicity: Discontinue immediately if signs and symptoms of hepatitis occur. (5.8)
- Clostridium difficile-associated diarrhea: Evaluate if colitis occurs.
 (5.10)

• QT Prolongation: Prolongation of the QT interval and isolated cases of torsade de pointes have been reported. Avoid use in patients with known prolongation, those with hypokalemia, and with other drugs that prolong the QT interval. (5.11, 7, 8.5)

----- ADVERSE REACTIONS -----

The most common adverse reactions ≥1% were nausea, diarrhea, liver function tests abnormal, vomiting, and rash. (6)

To report SUSPECTED ADVERSE REACTIONS, contact Bayer HealthCare Pharmaceuticals Inc. at [name] or FDA at [name] or www.fda.gov/medwatch.

----- DRUG INTERACTIONS -----

Interacting Drug	Interaction		
Theophylline	Serious and fatal reactions. Avoid concomitant use. Monitor serum level (7)		
Warfarin	Anticoagulant effect enhanced. Monitor prothrombin time, INR, and bleeding (7)		
Antidiabetic agents	Hypoglycemia including fatal outcomes have been reported. Monitor blood glucose (7)		
Phenytoin	Monitor phenytoin level (7)		
Methotrexate	Monitor for methotrexate toxicity (7)		
Cyclosporine	May increase serum creatinine. Monitor serum creatinine (7)		
Multivalent cationcontaining products including antacids, metal cations or didanosine	Decreased CIPRO absorption. Take 2 hours before or 6 hours after CIPRO (7)		

----- USE IN SPECIFIC POPULATIONS -----

See full prescribing information for use in pediatric and geriatric patients (8.4, 8.5)

See 17 for PATIENT COUNSELING INFORMATION and Medication Guide

Revised: 7/2016

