4.2 Exclusion Criteria

- 1. Presence of signs and symptoms suggestive of acute pyelonephritis: fever (temperature > 38°Celsius), chills, costovertebral angle tenderness, flank pain, nausea and/or vomiting
- 2. Receipt of prior effective antibacterial drug therapy for uUTI for the presenting illness unless the recovered pathogen demonstrates resistance to initial antibiotic and clinical symptoms persist
- 3. Concurrent use of non-study antibacterial drug therapy that would have a potential effect on outcome evaluations in patients with uUTI
- 4. Patients with ileal loops or urinary stoma
- 5. Patients with an indwelling urinary catheter in the previous 30 days
- 6. Patients with paraplegia
- 7. Patients who are likely to receive ongoing antibacterial drug prophylaxis after treatment of uUTI (e.g., patients with vesico-ureteral reflux)
- 8. Any history of trauma to the pelvis or urinary tract
- 9. Patient's urine culture results, if available at study entry, identify more than 2 microorganisms regardless of colony count or patient has a potential fungal pathogen
- 10. Patient's urine culture results, if available at study entry, identifies the causative uropathogen for the presenting illness to be resistant to ciprofloxacin
- 11. Patient has severe chronic kidney disease, or is receiving hemodialysis or peritoneal dialysis or had a renal transplant
- 12. Patient is known to have severe neutropenia

Clinical Trial Protocol: IT-004-401

- 13. Patient is known to be pregnant
- 14. Patients with uncontrolled diabetes mellitus
- 15. Patients with a known history of myasthenia gravis
- 16. Patients who require concomitant administration of tizanidine
- 17. Patients with a history of allergy to quinolones
- 18. Patient is considered unlikely to survive the study period or has a rapidly progressive or terminal illness including septic shock which is associated with a high risk of mortality

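### The appended label says to avoid ciprofloxacin with theophylline and in known QT prolongation or hypokalemia, but Protocol Sections 4.2 and 5.4.1 name none of these

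*Protocol*

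**What the plan says.** The label highlights in Protocol Appendix 4 contain two relevant entries. The theophylline row of the drug interaction table reads "Serious and fatal reactions. Avoid concomitant use. Monitor serum level (7". The QT bullet under Warnings and Precautions reads "Avoid use in patients with known prolongation, those with hypokalemia, and with other drugs that prolong the QT interval".

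Section 4.2 lists 18 exclusions. Three of them match items in the same label: "Patients with a known history of myasthenia gravis" (exclusion 15), "Patients who require concomitant administration of tizanidine" (exclusion 16) and "Patients with a history of allergy to quinolones" (exclusion 17).

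Section 5.4 contains three drug prohibitions: investigational drugs and magnesium- or aluminum-containing antacids (both Section 5.4.1), and systemic antibacterials that could affect the outcome evaluation (Section 5.4.2). Beyond these, Section 5.4.1 asks only that non-antibacterial medicines be kept to what the patient's care requires, and that they be recorded in the source document.

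Three other provisions bear on the point. Section 4 tells investigators to weigh all relevant conditions when judging suitability. Section 6.1 requires a medical history and a review of previous and concomitant drugs before the first dose. Section 6.4 lets the investigator withdraw a patient for safety.

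**The concern.** The protocol turns some label cautions into explicit entry criteria and leaves out others that carry the same instruction. Theophylline is the clearest case, because the label attaches fatal reactions to it and it is a medicine that a patient may need long term. The essential-medicine rule in Section 5.4.1 does not stop its use; it permits it. In a multicenter study without a written rule, each site decides for itself whether such a woman is treated.

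What is at stake is the safety of a small number of participants: serious or fatal reactions with theophylline, and the isolated cases of torsade de pointes that the label reports under QT prolongation. The response rates and their interpretation are not at stake.

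**Working it through.** The plan states no figure on this point and no calculation applies beyond counting. The check compares the label items with the protocol's rules.

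| Label item | Place in Appendix 4 | Protocol rule |
|---|---|---|
| Quinolone hypersensitivity | Contraindication | Exclusion 17 |
| Tizanidine | Contraindication: "Concomitant administration with tizanidine (4.2" | Exclusion 16 |
| Myasthenia gravis | Boxed warning: "Avoid CIPRO in patients with known history of myasthenia gravis" | Exclusion 15 |
| Magnesium or aluminum antacids | Interaction table (multivalent cation row): "Take 2 hours before or 6 hours after CIPRO (7" | Barred in Section 5.4.1 |
| Theophylline | Interaction table: avoid | None |
| Known QT prolongation | Warnings and Precautions: avoid | None |
| Hypokalemia | Warnings and Precautions: avoid | None |
| Other QT-prolonging drugs | Warnings and Precautions: avoid | None as such; a systemic antibacterial would come under Section 5.4.2 |

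1. *Count.* The four unmatched items in the last rows are named in 0 of 18 exclusions and 0 of 3 drug prohibitions. This shows that a rule is absent; it does not measure risk.

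2. *Contraindication was not the only threshold for exclusion.* Both label contraindications are exclusions. Myasthenia gravis is not a listed contraindication; it is an instruction to avoid the drug, and it is still excluded. The QT bullet is worded in much the same way.

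3. *A patient on essential theophylline.* Suppose that she meets inclusion criteria 1 to 4 and has none of the 18 listed exclusions. Her theophylline is not an investigational drug, an antacid or an antibacterial, so no prohibition in Section 5.4 applies. It is essential to her care, so the general rule allows it. No named criterion keeps her out. The same holds for a woman with known QT prolongation or known hypokalemia, since neither is listed.

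4. *Monitoring.* The theophylline row also asks for serum levels. Section 7.1.1 provides for no laboratory testing beyond urine, and the Schedule of Activities lists no ECG and no blood test. The study therefore does not supply the label's own fallback.

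5. *Length of a drug prohibition.* Two doses a day for 3 days is 2 × 3 = 6 doses, from Day 1 to Day 3, or to Day 4 when the first dose is taken in the evening.

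**The case against.** The best defense is that the label has tiers and the protocol follows them. The contraindications and the boxed-warning condition are exclusions. The QT and theophylline items stand lower, under precautions and interactions, and are left to the prescriber. The theophylline row even pairs its instruction with monitoring, which suggests that supervised co-use can occur. The highlights state that they are not the complete prescribing information, so how strictly each instruction is meant cannot be settled from the documents. The study uses a marketed drug at its labelled dose for 3 days, the label is attached, and the investigator must review history and drugs before dosing.

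Much of this stands, and it lowers the weight of the point. It does not remove it. The same safeguards applied to tizanidine and myasthenia gravis, for which explicit exclusions were still written, and the protocol gives no reason for the difference.

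The antacid rule is weaker support than it may look. Section 5.4.1 gives reduced bioavailability as its reason, so it does not show that the interaction table was screened for safety and a row missed.

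A reader might infer more than the documents support:

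- *That these women would be dosed.* The suitability clause in Section 4 and the Section 6.1 review give an investigator both the grounds and the information to keep them out.
- *That the protocol departs from the label's contraindications.* Both are exclusions.
- *That Section 7.1.1 forbids monitoring.* It describes study testing and does not bar clinically indicated care.
- *That every QT-prolonging drug should be an exclusion.* The highlights name no such drugs, and a list could narrow eligibility by an amount that cannot be judged here.

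**Conclusion.** The omission is confirmed. The attached label says to avoid ciprofloxacin with theophylline and in known QT prolongation or hypokalemia, and no named exclusion or drug rule covers any of the three. The essential-medicine allowance makes this more than a missing detail, because it lets the drug with the fatal-reaction warning through.

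The size is small. Affected women are probably few, but that is a judgment; the documents give no prevalence for any of these conditions or drugs. Partial safeguards exist. Sample size, analysis populations and efficacy estimates are untouched. The conclusion assumes only that the highlights in Appendix 4 are the label text that sites work from. It is a cheap improvement to patient safety and not a flaw in the study's ability to meet its objectives.

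**What to change.** In Section 4.2, add exclusions for current theophylline use, known QT prolongation and known uncorrected hypokalemia. In Section 5.4.1, prohibit theophylline from the first to the last of the 6 ciprofloxacin doses. For other QT-prolonging drugs, add a sentence in Section 5.4.1 that refers the investigator to the Appendix 4 warning, and leave any formal drug list to the sponsor.

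Apply all of this from the history and drug review already required in Section 6.1. No ECG, blood test, visit or CRF page is needed.

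The cost is a few lines of protocol wording and slightly narrower eligibility, by an amount that the documents do not allow to be estimated. Two limits remain. Without a blood test, hypokalemia is caught only when it is already known. Section 5.4.1 sends only antibiotics for the primary infection to the CRF, so compliance with the theophylline rule could be checked only in source records.

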Appendix 5 Summary of Changes

This summary of changes provides an overview of substantive changes and additions made for protocol IT-004-401 amendments. In addition, minor editorial revisions have been made for consistency.

General

• All Pages: Header

From: Amendment 01:08 November 2017 To: Amendment 02:27 March 2018

Study Procedures

- Section 4, 4.1-3, 4.1-4: clarification of; study population requirement of positive for both leukocyte esterase and nitrite dipstick, midstream specimen for diagnosis, informed consent process
- Section 5.2-1, 5.2-3: removal of additional language that does not apply to this study, clarification of site to collect at least the day and time of patients first dose taken during treatment follow up.
- Section 6.1: updated language to align with revisions to Section 4.
- Section 6.3.2: added requirement for Post Test of Cure (TOC) Day 21 (+/- 3 days) follow up call
- Section 9.2-5: clarified outcome assessment language
- Appendix 1 Schedule of Activities: Post Test of Cure (TOC) Day 21 (+/- 3 days) follow up call added
- Appendix 2 Microbiology: removed reference to requirement of long term storage of specimen at local lab
- Appendix 3: Revised Patient Assessment Symptom Questionnaire

1 INTRODUCTION

This document presents the Statistical Analysis Plan (SAP) for the IT-004-401, "A prospective, Phase 4 open label, multi-center study of the clinical and microbiologic efficacy of ciprofloxacin for the treatment of uncomplicated urinary tract infections in adult women." This plan contains definitions of analysis populations, derived variables and statistical methods for the analysis of clinical and microbiologic efficacy. The statistical plan described is an "a priori" plan, and the analyses outlined here have not been conducted prior to the preparation of this plan.

This SAP summarizes the design and objectives of protocol IT-004-401 and provides details of the definitions of the outcome measures and statistical methodology that will be used to analyze the data from the study. Any deviation from the planned analysis will be documented in clinical study report (CSR).

2 STUDY DESIGN

This prospective Phase 4 open label, multi-center study documents the clinical and microbiologic response of adult women patients with uUTI treated empirically with ciprofloxacin. Approximately 250 adult women with uUTI will receive oral ciprofloxacin 250 mg twice daily for 3 days.

The primary outcome measure for efficacy evaluation will be the overall response on Day 12 (+/- 1 day). For the primary efficacy evaluation, these percentages will be based on a microbiologic-modified intent to treat population (m-MITT). The m-MITT population will be comprised of all patients who received at least one dose of ciprofloxacin and had $\geq 10^5$ CFU/mL of a baseline pathogen isolated from a urine culture specimen taken at baseline, prior to initiation of ciprofloxacin therapy.

3 STUDY OBJECTIVES

3.1 Primary Objective

To evaluate the clinical and microbiologic response of patients with a uUTI treated with ciprofloxacin.

3.2 Secondary Objective

To evaluate the validity of specific tests found on the urine dipstick as a screening tool to identify symptomatic patients with a positive urine culture, defined as growth of $\geq 10^5$ CFU/mL of a uropathogen at baseline.

4 DEFINITION OF ANALYSIS POPULATION

The definition of analysis populations included in this study are below.

4.1 Intent-to-Treat (ITT) Population

All enrolled patients regardless of whether or not they received ciprofloxacin.

4.2 Modified Intent-to-Treat (MITT) Population

All patients in ITT population who received at least a single dose of ciprofloxacin.

4.3 Safety Population

All patients in ITT population who received at least a single dose of ciprofloxacin.

4.4 Micro-MITT (m-MITT)

All MITT patients with a positive study entry urine culture defined as $\geq 10^5$ CFU/mL of a uropathogen and no more than 2 species of microorganisms identified in the study entry urine culture, regardless of colony count.

4.5 Clinically Evaluable (CE)

Clinically evaluable is defined both at the end of treatment (EOT) and test of cure (TOC) visits.

- All patients who were included in the MITT population and meet the following criteria are clinically evaluable.
 - a) Received a minimum of four doses of ciprofloxacin.
 - b) Had no important protocol deviations that would affect the assessment of efficacy as indicated in the protocol deviation log (see section 7.9). These will be pointed out by clinical team and marked in the CE spreadsheet.
 - c) Had a Clinical response assessment of clinical cure or clinical failure (and not indeterminate) at the EOT or TOC visits (within Protocol visit window), respectively.
 Note: Since the PSAQ does not contain a date completed, the date if lab culture will be used.
 - d) Did not receive any antibiotic therapy with potential activity against any of the baseline uropathogens collected at screening between the time of the baseline culture and the EOT or TOC culture, respectively. This excludes the protocol defined study therapy and patients who were considered clinical failures and required additional antibiotic therapy. Patients with a coinfection with a gram-positive uropathogen resistant to ciprofloxacin are allowed to receive agents with narrow spectrum gram-positive coverage (i.e., such as linezolid or vancomycin).

Note: This rule will be applied through the manual review of CE spreadsheet by the sponsor.

